This application responds to **PAR-16-365:** "Pilot Clinical Trials for the Spectrum of Alzheimer's Disease and Age-related Cognitive Decline", and to this FOA's specific calls for **"Studies to define and refine the target population"** and **"Studies that address heterogeneity of response... identification of specific individuals... [who] are more likely or less likely to benefit from the intervention(s)"**.

For the past decade, the PI has assessed the acute neurophysiological effects of MEM, first in laboratory animals (107), and then in healthy human subjects (HS) and schizophrenia (SZ) patients (5,65,99,107), with the goal of using MEM or related drugs as pro-cognitive interventions in SZ. [Note: no investigators in this application have any financial relationship with the commercialization of MEM.] In the past 4 years, supported by the NIMH, these studies assessed the effects of acute MEM challenge (placebo (PBO), 10, 20 or 30 mg, po) on measures of **early auditory information processing (EAIP)** and neurocognition in SZ patients and HS. Prepulse inhibition (PPI), mismatch negativity (MMN) and gamma band auditory steady-state response (ASSR) were used as dependent measures because they: 1) are neurophysiological measures of EAIP, i.e. of the brain's automatic response to a simple sensory event proximal to, or independent of, a point at which it engages conscious or volitional processing; 2) are reliable, objective and quantitative; 3) consistently detect deficits in neuropsychiatric populations; 4) reflect "automatic" vs. volitional processes and are relatively insensitive to motivational or effort-based artifact; 5) are suited to repeated testing in a cross-over design without significant order or carry-over effects, and 6) are each regulated by NMDA activity, with at least some evidence for enhanced performance associated with MEM (29,44,107), including the PI's studies demonstra-

ting MEM-enhanced PPI in HS (107), and those of others reporting MEM-enhanced MMN (44) in HS.

[figure not shown]

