Fig. 2. Effects of MEM on A: PPI; B: MMN; C, D: ASSR in HS and SZ patients. Patients and HS (n's=42 & 42) were tested after 1 pill of either PBO or MEM (10 or 20 mg po; 20 mg shown here) in a double-blind, balanced cross-over design. Tests were 7d apart. Compared to HS, patients had deficits in MMN (B) and ASSR (C,D). MEM (20 mg) significantly enhanced PPI (99) (A; p<0.04 for 10-120 ms; p<0.01 for 60 ms), MMN (99) (B; p<0.014; stimulus “mismatch”: Duration; Pitch; Combined) and ASSR (65) (C: evoked power, 40 Hz *p<0.025; D: gamma phase locking, *p<0.002). An identical test design is proposed for the present study, to identify “MEM-sensitive” patients with AD.

[figure not shown]
Via a placebo (PBO)-controlled within-subject cross-over design, we detected statistically significant effects of MEM (20 mg) on PPI, MMN and ASSR (65,99) (Fig. 2A-D). In each case, one pill of MEM significantly enhanced EAIP. These changes were not explained on the basis of AP medication interactions, or other factors related to treatment or illness chronicity, since similar changes **were detected in both patients and HS**, as we had previously reported in HS with PPI (107), and **as others had previously reported in HS with MMN** (44).

This is the first demonstration that deficient PPI, MMN and ASSR in SZ patients – widely viewed to reflect fixed, heritable abnormalities in brain mechanisms regulating auditory information processing – can be significantly enhanced (i.e. brought significantly closer to normal values) via an acute intervention in chronically ill SZ patients. These findings of MEM-enhanced EAIP are novel and important, as they demonstrate significant plasticity in brain mechanisms that are thought to contribute to “core” neurocognitive deficits in SZ. Because EAIP are known to mediate neurocognition and function in these patients (111), in a separate application, we hope to use these findings to identify novel therapeutic strategies for SZ and related disorders.

Ironically, this approach has faced some headwinds, based on a concern that use of an NMDA antagonist in SZ patients might lead to symptom exacerbation; this concern persists in peer review despite numerous controlled trials and meta-analyses of the use of MEM as an adjunctive therapy in SZ, all showing that it is well-tolerated, and most demonstrating clinical benefits (cf. 127). Clearly, this pattern of safety and tolerability parallels the clinical experience with MEM in AD populations (37-8).

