C. Approach: This application will test the acute effects of 20 mg MEM (po) on EAIP in patients with mild-to-moderate severity AD (**Mini-Mental State Examination score between 10-22 at screening**), and determine whether sensitivity to MEM-induced changes in primary EAIP measures predicts the clinical response to MEM in these patients over a 24-week trial. The primary clinical outcome measure will be the Alzheimer's Disease Assessment Scale (ADAS-cog) (87), as described below. *Secondary analyses will assess alternate potential biomarkers, alternate outcome measures, and moderating roles of specific patient characteristics (including genotype), as well as the anatomical localization of the MEM-induced changes in EAIP measures.*

Aim 1. *To assess the acute effects of MEM (0 vs. 20 mg) on measures of early auditory information processing (EAIP) in patients with mild-to-moderate severity AD.* Measures of PPI, MMN and ASSR will be assessed in 88 individuals with mild-to-moderate severity AD after placebo (PBO) and 20 mg MEM po, in a double-blind, randomized order cross-over design. **Hypothesis 1:** Assessed across the full cohort of patients, PPI, MMN and ASSR will be significantly greater after MEM vs. PBO. However, the response to MEM will be heterogeneous: the magnitude of this “MEM effect” (MEM minus PBO) will vary across the dependent measures, and across patients, with some patients demonstrating robust increases in EAIP measures after MEM, and other demonstrating little response or reduced EAIP performance.

Aim 2. To determine the ability of MEM-induced alterations in EAIP in AD patients to predict their clinical response to MEM. The magnitude of the “MEM effect” will be calculated for each patient and each EAIP measure. MEM treatment will be initiated and titrated to 10 mg bid in all patients. Clinical severity will be assessed at baseline, 8, 16 and 24 weeks using the ADAS-cog as a primary measure. Analyses will determine whether the MEM effect on some or all EAIP measures moderates the magnitude of the clinical response to MEM. **Hypothesis 2:** Patients exhibiting a larger “MEM effect” on EAIP measures will exhibit a more robust positive clinical response to MEM, compared to patients exhibiting a smaller MEM effect on EAIP measures. This hypothesis will be tested empirically for each of the EAIP measures, and for regression-derived composite scores from multiple EAIP measures.

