A **comprehensive neuropsychological evaluation** is conducted under the supervision of [name] (\approx 2h; see "Human Subjects"). This test battery is used to characterize "MEM-sensitive" vs. "-insensitive" subgroups, and includes sensitive measures of memory (California Verbal Learning Test-II, WMS-IV Visual Reproduction Test with delayed recall and recognition, WMS-IV Logical Memory with delayed recall and recognition), attention (WAIS-R Digit Span Forward and Backward), language (Boston Naming Test; Letter and Category Fluency Tests), problem solving and executive function (modified Wisconsin Card Sort Test, Digit Symbol Substitution Test; Trailmaking, Fluency Switching, and Color-Word Interference subtests of the Delis-Kaplan Executive Functioning System [DKEFS]); constructional and visuospatial abilities (WASI-II Block Design Test, Clock Drawing Test, D-KEFS Visual Scanning), and global cognition (Mattis Dementia Rating Scale-2). Appropriate normative data are used for all tests (eg., Mayo Older American Normative Studies; 98). The number of prior cognitive assessments will be recorded for each subject to ensure that experimental groups (MEM-sensitive vs. MEM-insensitive) do not differ in the number of prior assessment exposures. A follow-up visit with the primary provider is scheduled for approximately 2-3 weeks after screening. All subjects are paid after screening, test days and 8, 16 and 24-week follow-ups (see "Human Subjects").

Test Days: Subjects who complete the **screening session** are scheduled for **EAIP Test Days** within 7 days. Transportation is provided. Urine toxicology is repeated on each test day. Test Days last from 0830–1600, much of which is spent relaxing, watching television, reading or eating. In brief, EAIP are assessed as in (59,99), 210 (PPI) and 345 min (MMN, ASSR) after administration of placebo or MEM (20 mg po), in a randomized order double-blind design. Vital signs (VS) and visual analog scale (VAS) measures of subjective self-ratings (99) are taken throughout the day. MEM pharmacokinetics are linear for single oral doses of 5-40 mg; T_{max} for a single 20 mg dose is 6.89 h; elimination $T_{(1/2)}$ is 60-80 h (94). Test days are \approx 1 week apart.

A.	\approx Day	B. Screen Day	C. Test Days a.m.	D. Test Days p.m.
Screen Day	1	Consent, Structured history	830: Brkfst, vital signs, UTox	VS, VAS cont'd
Test Day 1	8	Baseline clinical metrics	900: Pill (PBO or MEM)	1230: PPI (30 min)

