Aim 1 tests EAIP MEM sensitivity in patients with mild-to-moderate severity AD, in a double blind, within-subject cross-over design of MEM (20 mg po) vs. PBO. The primary result of Aim 1 is a biomarker characterization of "EAIP MEM-sensitivity" for each subject. Patients are also screened for baseline outcome and neurocognitive measures. In Aim 2, all patients titrate to 10 mg MEM bid, and outcome measures are collected at 8, 16 and 24 weeks. Analytic strategies are then used to test the hypothesis (H2) that greater EAIP MEM sensitivity predicts greater clinical MEM sensitivity.

Detailed Methods:

Stimulus parameters: The rationale for startle and ERP stimuli reflects both **empirical** and **theoretical** considerations, as discussed in our published reports (99,103). Empirically, these stimuli and session designs detect consistent MEM effects on PPI, MMN and ASSR (Fig. 2), and thus afford us the strongest predictions in terms of MEM effects in this application. There are also pragmatic considerations specific to each measure; for example, weaker pulse intensities generate smaller startle responses, and with the habituation resulting from repeated testing (2 test days), this results in an unacceptable number of startle "non-responders". Space does not allow a full description of the many such decision points with each measure, which are supported by a rich literature and the PI's and Co-PI's > 30 years of published experience.

Startle and PPI are assessed as in (99), with 42 trials, of 6 types: a 118 dB(A) 40 ms noise (pulse), and pulse preceded 10, 20, 30, 60, or 120 ms by a prepulse 16 dB over a 70 dB(A) background. Primary measure: **MEM effect (MEM minus PBO) on mean %PPI with 60 ms prepulse intervals**. Total time: 30 min, with clean-up.

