Aim 1: Repeated measure (Rm)-ANOVAs will determine whether PPI, MMN and ASSR significantly differ after MEM vs. PBO (Hypothesis 1). Primary variables for each EAIP, as well as exploratory "secondary" measures, are identified above. Based on a recruited sample of 88 total participants, we will have 80% power to detect effect sizes of $d = 0.35$ (small) using a Bonferroni corrected $\alpha = .05/3$ (2-tail). Heterogeneity of response will be characterized using variance components expressed as intraclass correlation coefficients (ICCs).

Aim 2: Linear mixed-effects models regressing change in ADAS-cog outcome scores (at 8, 16, and 24 weeks vs. baseline) onto a fixed effect of group defined by MEM sensitivity will test the hypothesis that patients exhibiting a larger "MEM effect" on EAIP measures will exhibit a larger positive clinical response to MEM. Groups will be defined by a median split of "MEM effect" (MEM minus PBO) on EAIP. Power was estimated using methods described by Hedeker et al. (25) solving for sample size with $\alpha = .05$ (2-tail), test-retest correlations of .50, and 5% attrition at each time point. A sample of 88 total participants provides us with 80% power to detect a medium effect of $d = 0.50$. The primary outcome will be chosen based on effect sizes obtained as part of Aim 1. In exploratory analyses, we will also examine group by time interactions using orthogonal polynomial contrasts. We will also predict change in clinical outcomes as a function of all four candidate biomarkers in order to create an optimal prediction equation. We will perform ROC curve analyses using EAIP MEM sensitivity values as continuous variables and predict clinical improvement after MEM as a discrete outcome (responders vs. non-responders) in order to determine the clinical utility of this approach defined in terms of sensitivity and specificity. Secondary analyses will also be conducted with biomarker groups defined as "MEM-sensitive vs. -insensitive" via specific thresholds for EAIP MEM sensitivity.

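### The randomised cross-over names no period or sequence term and the biomarker is a raw drug-minus-placebo difference, so any test-day shift would add noise to H2 (low priority)

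*Combined protocol and SAP*

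**What the plan says.** Under Approach, Aim 1 is a "double-blind, randomized order cross-over design"; the Test Days section repeats that dosing is given "in a randomized order double-blind design", with test days about a week apart. The sequence ratio is not stated for this trial. The Fig. 2 legend describes the earlier work as run "in a double-blind, balanced cross-over design" and adds: "An identical test design is proposed for the present study".

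Under Statistical tests for each hypothesis, the Aim 1 test reads: "Repeated measure (Rm)-ANOVAs will determine whether PPI, MMN and ASSR significantly differ after MEM vs. PBO (Hypothesis 1"). The Aim 2 grouping reads: "Groups will be defined by a median split of 'MEM effect' (MEM minus PBO) on EAIP". Neither statement, nor the General Approach paragraph, names period, test day or sequence. Sex is the only factor assigned to all major analyses (Sex as a biological variable).

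The overview with Fig. 10 shows how much rests on the individual score: "The primary result of Aim 1 is a biomarker characterization of" each subject's sensitivity to the drug.

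On order effects, the Significance section says the measures "are suited to repeated testing in a cross-over design without significant order or carry-over effects".

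**The concern.** In an ordinary two-period cross-over, a test-day shift cancels from the treatment mean when the sequences are balanced, so leaving out period costs only precision. Here the single-patient difference is itself the product of Aim 1 and the predictor in H2, and nothing cancels within one patient. If the measure drifts by s from day 1 to day 2, a patient who takes memantine on day 2 scores the true effect plus s, and a patient who takes it on day 1 scores the true effect minus s. Patients near the median can then be classed as sensitive or insensitive partly by the order they were allocated. At stake are the power of the H2 split, the precision of Aim 1, and any threshold derived from the raw scores.

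**Working it through.** **Inputs from the plan** (Statistical tests for each hypothesis): N = 88. Aim 1: d = 0.35, two-sided α = 0.05/3, 80% power. Aim 2: d = 0.50, two-sided α = 0.05, correlation 0.50, three follow-up visits, 5% attrition per time point, 80% power. **Assumed:** the shift s (day 2 minus day 1, in SD of the drug effect), because no section gives one.

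**Reproducing the plan.** Aim 1, paired t with 87 df and noncentrality 0.35 × √88: power 79.8%. Aim 2, two-group repeated-measures formula with visit retention 1 + 0.95 + 0.9025 = 2.8525: n per group = 2 × (1.960 + 0.842)² × (1 + 2 × 0.50) / (0.50² × 2.8525) = 44.03, or 88 in total. Both stated figures stand.

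**Effect of a shift on the raw split.** Let the true effect be T ~ N(0,1) and the observed score T + s or T − s, 44 patients each.
- Patients on the wrong side of the median: 88 × (Φ(s) − 0.5).
- Attenuated H2 effect: d = 0.50 × exp(−s²/2).
- H2 split power: Φ(2.8016 × d/0.50 − 1.96), where 2.8016 is the value giving 80%.

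**Effect on Aim 1 without a period term.** Under simple randomisation the SD of the differences becomes √(1 + s²), so d = 0.35/√(1 + s²), entered in the noncentral t. The balanced-order column is simulated.

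| s (SD) | Patients moved, of 88 | H2 d | H2 split power | Aim 1 power, simple randomisation | Aim 1 power, balanced 44/44 |
|---|---|---|---|---|---|
| 0 | 0 | 0.500 | 80.0% | 79.8% | 79.7% |
| 0.10 | 3.5 | 0.498 | 79.6% | 79.4% | 79.4% |
| 0.20 | 7.0 | 0.490 | 78.4% | 78.0% | 78.3% |
| 0.35 | 12.0 | 0.470 | 75.0% | 74.3% | 75.2% |
| 0.50 | 16.8 | 0.441 | 69.6% | 68.9% | 70.7% |

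With a period term, simulated Aim 1 power stays at 79.7-79.8% (balanced) or 79.3-79.4% (simple randomisation) at every shift.

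**Continuous H2 test.** Assume a linear biomarker-outcome relation, calibrated so the split has about 80% power (about 78% with a t reference). The raw continuous test then has about 93% power at s = 0, 90% at 0.35 and 87% at 0.50.

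**Effect of adjusting the split.** Centring the difference within sequence before taking the median moves about 3.0 of 88 patients at every shift, because the sequence means are estimated. The raw split moves the same number at about s = 0.085. Simulated H2 split power is 79.1% at every shift after centring, against 79.4% (s = 0) and 67.9% (s = 0.50) for the raw split. The simulated raw values run 0.6 to 1.7 points below the closed form in the table; the comparison of raw with centred is made within the simulation.

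**Residual drug.** With the stated half-life of 60-80 h and 168 h between test days, the fraction left is 2^(−168/60) = 0.14 to 2^(−168/80) = 0.23, or 2.9 to 4.7 mg of a 20 mg dose.

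**The case against.** The strongest reply is that the harm is hypothetical and that much in the documents argues against it. The Significance section reports no significant order or carry-over effects. The Measures of EAIP section calls MMN highly stable. Potential Limitations says age and symptoms should not limit these measures and cites experience in 20 AD patients. The residual 2.9-4.7 mg is below the 10 mg that the section on the choice of 20 mg reports as inactive on all three measures. Silence about a model term is also weak evidence, since the same section does not name sex although another section puts it in all major analyses.

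Most of this stands, and it is why the point ranks low. Two things remain. Absence of a significant order effect is not a bound. If that statement rests on the Fig. 2 sample (an assumption: 42 to 84 subjects), power to have detected a shift was about 24-44% at 0.20 SD, though 89-99.5% at 0.50 SD. And the documents give reasons for doubt: the stimulus-parameters text acknowledges habituation over the two test days (of startle size; %PPI is a ratio and need not follow), and Potential Limitations concedes that diagnosis and age both differ from past experience.

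A further fair objection is that centring is not free when the shift is near zero, and that it ties each score to sample means, which fits awkwardly with a two-visit test for one patient. That is a reason to show both splits.

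A reader might go further and infer that the omission biases Aim 1, manufactures an H2 association, or shows that period will be ignored. The documents support none of these. Randomised order rules out a systematic association and leaves a balanced mean unbiased. The general linear and mixed model framework can take the term, and the cited analyses cannot be checked. What can be said is that the term is not named.

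**Conclusion.** The point holds as a low-priority improvement to the analysis. The plan randomises order but names no use of it, and its key predictor is a raw difference that absorbs any test-day shift. Up to about 0.20 SD the loss is under 2 points of power in either aim, which is negligible. It becomes material, at about 5 points for 0.35 SD and 10 to 11 points for 0.50 SD, only if the shift is as large as the drug effect Aim 1 is powered to find, and nothing in the documents shows a shift of that size. These figures rest on an assumed shift, normal scores and 1:1 sequences, and the H2 losses apply to the median split. If the realised sequences are unequal, the unadjusted Aim 1 mean is off by s × (n₁ − n₂)/N, for example 0.09 × s at 48:40. The case for acting is the asymmetry: a few tenths of a point if there is no shift, against roughly 11 points of simulated split power regained at 0.50 SD (67.9% to 79.1%). N = 88 is not wrong.

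**What to change.** - **Aim 1:** include period and sequence in the model, and report the period estimate with its 95% CI. With 88 patients the half-width is t(0.975, 86)/√88 = 0.21 SD, so an estimate near zero would rule out a shift of 0.35 SD.
- **Continuous H2 model:** include sequence as a covariate.
- **Median split:** pre-specify a score adjusted for the estimated period effect before patients are grouped, and report the raw and adjusted splits side by side. A sequence covariate added afterwards does not repair a split already made on raw differences.
- **Thresholds:** any cut-off offered for use in single patients must state the period correction behind it.

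**Cost:** SAP wording and 1-2 df. If the true shift is zero, Aim 1 loses about 0.01 points (balanced order) to 0.6 points (simple randomisation), the H2 split loses about 0.3-0.4 points, and about 3 of 88 patients change group relative to the raw split. Adjustment removes the average of any residual-drug effect but not its variation between patients, and a two-period design cannot separate carry-over from sequence.
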